## **Secondary Objectives**

To assess whether early intervention with Favipiravir improves mortality in patients with COVID-19 infection

To determine whether early intervention with Favipiravir reduces resource utilisation in patients with COVID-19 infection

To explore whether early intervention with Favipiravir attenuates the excessive inflammatory cytokine response in patients with COVID-19 infection

- Clinical status as assessed with the seven-category ordinal scale at day 7 and day 14 (postrandomisation)(19)
- 2. Change in clinical status as assessed with the sevencategory ordinal scale at day 7 and day 14 (postrandomisation) relative to baseline(10)
- 3. All-cause in-hospital mortality
- Time to clinical response defined as:
   Time to 2 point reduction (maintained for 24 hours) in total NEWS2 (National Early Warning Score 2) compared to baseline NEWS2 taken at Randomisation(11)
- 5. Time to 2 point reduction (maintained for 24 hours) in the NEWS2 (National Early Warning Score 2) component compared to baseline NEWS2 taken at Randomisation for each of the following:
  - Temperature
  - Heartrate
  - Respiratory rate
  - Oxygen saturations(11),
- 6. Number of participants requiring intensive care admission
- 7. Duration of intensive care admission
- 8. Number of participants requiring mechanical ventilation
- 9. Duration of mechanical ventilation
- Number of participants requiring non-invasive ventilation, continuous positive airways pressure or high-flow oxygen via (Optiflo®, Airvo system or equivalent)
- 11. Percentage of progression in supplemental oxygen requirement at day 7
- 12. Number of participants readmitted to hospital (all-
- 13. Proportion of patients with culture confirmed bacterial or fungal infection
- 14. Changes in host inflammatory profiles at postrandomisation time points, relative to baseline

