#### 7. TRIAL DESIGN

The study is an open-label, two arm, multi-centre randomised controlled clinical trial, to investigate the clinical effectiveness, safety, and resource utilisation of early treatment intervention in patients admitted to hospital with a suspected or proven COVID-19 infection. Subjects will be randomised 1:1 to one of two arms to receive:

- Arm 1: Favipiravir + standard of care
- Arm 2: Standard of care

The study treatment duration will be 10 days for each participant. If a participant recovers sufficiently to be discharged home before day 10, favipiravir will be supplied and the regimen completed as an outpatient.

Samples will be collected at three timepoints: baseline, between days 5 to 10 and days 14 to 28 (see section 9.4). In such instances where participants recover sufficiently to be discharged home and are not in hospital at the latter sample collection timepoints, they will be invited to return to facilitate this (provided that they are well enough and maximally twice).

For further information on activities at visits and schedule see Section 8.

Participants will exit the study at day 28 or if they become deceased.

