#### 10.2. Inpatient Data Collection

Whilst patients are hospitalised all routine data, including laboratory test results, procedures and medication will be collected as necessary, as part of the trial from day 0 to day 28 or until discharge, whichever is sooner. Change in ordinal score lasting >24 hours will be recorded. If patients are readmitted within the 28-day period, data will also be collected from this second admission until 28 days post-study commencement.

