#### 13. STATISTICS AND ANALYSIS

### 13.1 Description of Statistical Methods

The two arms (Favipiravir vs Standard of Care) will be compared with time-to-event analysis using a competing-risks survival regression based on Fine and Gray's proportional subhazards model. All analysis will be performed on an intention to treat basis.

Patient improvement will be monitored for 28 days or until death. It is not expected that any patient will be lost to follow-up, even if discharged home. Kaplan-Meier plots will be constructed showing the probability of survival in each treatment group. Schoenfeld Residuals will be plotted and tested over time to examine the assumption of proportional hazards; with a restricted mean survival time analysis (RMST) as an alternative method for analysis for the proportional hazards assumption is not met.

Similarly, patients who discontinued the clinical trial or administration of the study drug due to worsening of symptoms/lack of efficacy (including patients who switched to rescue therapy) but remain alive will be handled as cases right-censored as of day 28, with no clinical improvement.

Additional secondary analysis of the primary outcome will be undertaken that adjust for, or involves a sub-set of patients, and examines the effect of

- (a) country of recruitment
- (b) time from onset of symptoms (median split)
- (c) limited to those patients with confirmed SARS-COV-2 infection
- (d) by high or low (median split) viral load.
- (e) early or late during recruitment to the study to examine improves in clinical care and understanding.

Other secondary analysis have been pre-specified in the statistical analysis plan and listed on clinical trials.gov. Differences between the two trial arms will be compared by standard and appropriate statistical tests.

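### The intensive care and ventilation durations (secondary endpoints 7 and 9) take no account of death, so a difference between arms cannot be read as benefit

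*Protocol*

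**What the plan says.** The secondary endpoint list in protocol Section 6.4 includes "Duration of intensive care admission" (endpoint 7) and "Duration of mechanical ventilation" (endpoint 9), with nothing further on either. The table does not pair endpoints with objectives line by line, but these two plainly serve this one: "To determine whether early intervention with Favipiravir reduces resource utilisation in patients with COVID-19 infection". Shorter is therefore the favourable direction.

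Mortality is a separate item, "All-cause in-hospital mortality" (endpoint 3), and no text links it to the durations. Section 7 states: "Participants will exit the study at day 28 or if they become deceased". Section 10.2 collects inpatient data "as part of the trial from day 0 to day 28 or until discharge, whichever is sooner", with readmissions also followed to day 28.

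On analysis, Section 13.1 says the arms will be "compared with time-to-event analysis using a competing-risks survival regression based on Fine and Gray's proportional subhazards model". The text around that sentence concerns clinical improvement. For other endpoints it refers to the statistical analysis plan and adds: "Differences between the two trial arms will be compared by standard and appropriate statistical tests". The protocol does not say how a death in intensive care or on a ventilator counts, or which participants contribute to endpoints 7 and 9.

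**The concern.** A stay in intensive care or a period of ventilation can end in recovery or in death. A raw duration treats the two alike. If patients who die do so sooner than survivors recover, extra deaths shorten the mean and look favourable, and deaths prevented can lengthen it and look unfavourable.

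The choice of denominator does not remove the problem:

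- **Only patients admitted to intensive care or ventilated.** The comparison is between groups formed after randomisation, possibly by treatment.
- **All randomised patients, with zero for those never admitted or ventilated.** A patient who dies without reaching intensive care or a ventilator receives the best possible value.

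Under either reading, stays still running at day 28 are cut there. At stake is the interpretation of two of the main measures of resource use, in a trial that also sets out to judge clinical effectiveness.

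**Working it through.** The protocol gives no figure for these endpoints, so there is nothing to reproduce. The check is of direction, under assumed rates.

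**Two-point illustration (ventilated patients, ventilation starting at day 0).** Let p be mortality, D the ventilated days of those who die and S those of survivors. All three are assumed.

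- Mean duration = pD + (1 − p)S, so a change Δp in mortality moves it by Δp(D − S).
- Ventilator-free days to day 28, with death scored 0 = (1 − p)(28 − S), so the same change moves them by −Δp(28 − S).

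Deaths sooner than recovery (D = 7, S = 14), p from 0.40 to 0.50:

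- Duration: 0.4×7 + 0.6×14 = 11.2, against 0.5×7 + 0.5×14 = 10.5 days. This looks better.
- Ventilator-free days: 0.6×14 = 8.4, against 0.5×14 = 7.0. This shows the harm.

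Deaths later than recovery (D = 14, S = 10), same change in p:

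- Duration: 0.4×14 + 0.6×10 = 11.6, against 0.5×14 + 0.5×10 = 12.0 days. The direction reverses.
- Ventilator-free days: 0.6×18 = 10.8, against 0.5×18 = 9.0. Still the correct direction.

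The sign for raw duration thus depends on whether D is below or above S. The sign for free days does not.

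**Second model.** Assume constant daily hazards of liberation (l) and death (d), capped at 28 days, with h = l + d.

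- Mean duration = (1 − e^(−28h))/h.
- Death on the ventilator by day 28 = (d/h)(1 − e^(−28h)).
- Ventilator-free days = l[28/h − (1 − e^(−28h))/h²], ignoring deaths after liberation.

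With l = 0.06:

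| d per day | Mean duration (days) | Death on ventilator | Ventilator-free days |
|---|---|---|---|
| 0.02 | 11.2 | 22.3% | 12.6 |
| 0.04 (reference) | 9.4 | 37.6% | 11.2 |
| 0.08 | 7.0 | 56.0% | 9.0 |

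Doubling the death hazard shortens the duration, and halving it lengthens it. Over l = 0.04 to 0.08 and d = 0.02 to 0.04:

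| Death hazard | Mean duration (days) | Death on ventilator |
|---|---|---|
| Reference | 8.0–13.6 | 19–45% |
| ×1.5 | 7.0–12.3 | 26–56% |
| ×2 | 6.2–11.2 | 32–64% |

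**How often a test would mislead.** In 4,000 simulated trials per setting (l = 0.06, d = 0.04 in the control arm), a two-sided 5% Wilcoxon test on raw duration favoured the arm with the doubled death hazard in 16%, 29% and 42% of trials, with 25, 50 and 75 ventilated patients per arm. With the hazard multiplied by 1.5 the figures were 7%, 11% and 16%. With no difference they were 2–3%. The numbers ventilated are also assumptions.

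**The case against.** **The analysis plan may settle this.** The handling of deaths, the denominator and stays running at day 28 are often left to the SAP, which is not shown. That stands as a limit: silence in the protocol is not a fixed bad rule. It does not remove the point, because what the protocol itself fixes is the raw duration, and a choice of test does not alter what that measures.

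**Fewer bed-days through death really is lower resource use.** Correct, and the background in Section 5 cites saturated intensive care beds and ventilators. The durations are legitimate as utilisation measures. The error lies in reading a shorter duration as benefit, which the protocol does not instruct but does nothing to prevent.

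**Mortality is visible elsewhere.** Endpoint 3 reports it, endpoints 1 and 2 include death as category 7, and the monitoring board considers mortality evidence (Section 16.1). A careful reader could detect a conflict, although nothing requires the results to be read together.

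**Stronger readings that the documents do not support.**

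- That the endpoints always favour the deadlier arm: the D = 14, S = 10 case shows otherwise, and the consistent direction in the second model holds only for constant hazards with the death hazard alone changed.
- That the protocol compares only ventilated or intensive care patients: it names no subset, and Section 13.1 puts all analysis on an intention-to-treat basis.
- That it deliberately keeps competing-risks methods from these endpoints: the Fine and Gray sentence names no endpoint, and its link to improvement is inferred from context.

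**The alternative has weaknesses.** Free days answer a different question and keep the day-28 cut-off. With death scored 0, an early death in a patient never ventilated ties with a survivor ventilated for all 28 days. These points justify keeping the durations beside the composite.

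**Conclusion.** The point holds in a limited form. Endpoints 7 and 9 are raw durations with no account of death, and a between-arm difference in them cannot be read as benefit in either direction. Its size cannot be derived from the protocol. Under the assumed two-point case, 10 percentage points more mortality shortens mean ventilation by 0.7 days (11.2 − 10.5) while costing 1.4 ventilator-free days (8.4 − 7.0). With deaths later than recovery, the duration instead rises by 0.4 days (12.0 − 11.6). All these figures describe ventilated patients only; differences averaged over all randomised participants would be diluted by those never ventilated. The endpoints are secondary and mortality is reported separately, so the primary conclusion is not at risk. The change is still worth making, because the remedy is inexpensive.

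**What to change.** - Keep endpoints 7 and 9 as descriptive measures of resource use, and show them by arm and by survival status.
- Base the between-arm comparison on days alive and out of intensive care, and days alive and free of mechanical ventilation, to day 28 in all randomised participants. Score death by day 28 as the worst value; a category below zero days avoids the tie with survivors treated throughout.
- Analyse by a rank or proportional-odds method, with mortality and the duration components shown alongside.

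**Cost.** A change to endpoint and SAP wording; the intensive care and ventilation dates are already needed for endpoints 7 and 9. The composite mixes mortality with duration, which is why the components must accompany it. Vital status to day 28 must be confirmed for discharged patients: Section 10.2 stops at discharge unless there is a readmission, the telephone interview in Section 10.3 covers those discharged before day 10, and endpoint 3 counts in-hospital deaths only. Section 13.1 already expects follow-up for 28 days or until death. The protocol version is dated April 2021, in an open-label trial that began in May 2020, so the free-day measures should be documented as dated additions, made before outcome data by arm are examined, and not as replacements for the existing endpoints.

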## 9.6. Potential Risks

The following are known side-effects of the investigational medical product:

Favipiravir	
Common	Raised uric acid level (4.8%); diarrhoea (2.3%); reduced neutrophil count (1.8%); raised liver enzymes (1.6%); nausea (2.1%); urinary tract infection (1.5%), headache (1.1%), vomiting (1.0%), blood triglycerides increased (1.9%)
Uncommon or Rare	Confusion; fulminant hepatitis; renal failure; agranulocytosis; Steven- Johnson syndrome (toxic epidermal necrolysis)
Cautions	Participants on theophylline, pyrazinamide, repaglinide, or famiciclovir should be treated with caution due to drug interactions

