## 12.2. Adverse Events (AEs) Definition

For the purposes of this study, any non-COVID-19 related untoward medical occurrence, either newly acquired or worsening of a current AE, in a patient or clinical trial participant administered a study intervention whether or not considered related to the study intervention.

An AE can therefore be any unfavourable and unintended non-COVID-19 related sign (including an abnormal laboratory finding), symptom, or disease (new or exacerbated) temporally associated with the use of a study intervention.

Events meeting the AE definition for this study:

- Any non-COVID-19 associated abnormal laboratory test results (haematology, clinical chemistry, or urinalysis) or other safety assessments (e.g., Electrocardiogram, radiological scans, vital signs measurements), including those that worsen from time of consent
- Any non-COVID-19 associated exacerbation of a pre-existing condition including either an increase in frequency and/or intensity of the condition.

- Any new non-COVID-19 associated conditions detected or diagnosed after the study intervention has been administered to the participant.
- Symptoms, or the clinical sequelae of a suspected drug-drug interaction.

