## 12.6. Collecting and Recording AE and SAE

- All non-COVID-19 associated AEs and SAEs, whether or not they are related to the study intervention or protocol defined procedures must be documented in the patients' medical notes and eCRF. If no diagnosis is available, the Investigator should record each sign and symptom as individual AEs.
- The site will enter the AEs and SAEs into the eCRF as soon as it is known to the Investigator or sub investigator. The eCRF must be updated as soon as additional information is made available to the investor or sub investigator. If the electronic system is unavailable for more than 24 hours, then the site will use the paper form
- Reportable SAEs as defined above will be reported to the Co-Sponsor within 24 hours of the study team becoming aware of the event. SAE details will be included in the Safety Event Report Form (SERF) and the SERF emailed to [contact] or faxed to [name].
- The AEs and SAEs reporting period will be from participant consent until 28 days after randomisation.
- Pregnancy will be also subjected to the same reporting rules of SAE. Pregnancy details will be included in the SERF and the SERF emailed to [contact] or faxed to [name] within 24 hours of the study team becoming aware of the pregnancy.
- All AEs and SAEs will be followed up until resolved or the participant's participation in the study ends (i.e. until the final CRF is completed for that participant).
- When an AE/SAE occurs, it is the responsibility of the investigator or sub investigators to review all clinical information relating to the event.
  - The investigator or sub investigator will attempt diagnose the event based on direct examination and/or other clinical information.
  - The principle investigator must confirm within the SERF the causality assessment with the study drug. If the SAE is assessed as possibly related, probable related or definitely related, the principal investigator must also confirm the event expectedness versus the Reference safety information (refer to section 12.10).
- The Investigator must record follow-up information (related to the reported event) by updating the patient's medical records and the appropriate forms in the (e)CRF. The worst-case severity and seriousness of an event must be kept throughout the trial.

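### Secondary endpoint 13 (culture-confirmed infection) has no stated window, and routine capture of culture results stops at discharge, so ascertainment depends partly on length of stay

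*Protocol*

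**What the plan says.** Section 6.4 gives endpoint 13 as "Proportion of patients with culture confirmed bacterial or fungal infection". No window and no data source are attached. Endpoints 1, 2 and 11 in the same list are tied to day 7 or to days 7 and 14, and endpoint 3 is limited to hospital by its wording ("All-cause in-hospital mortality").

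Section 8.8 keeps every participant on study for 28 days from randomisation. Section 10.2 collects routine data, laboratory results among them, "from day 0 to day 28 or until discharge, whichever is sooner". For a patient who is readmitted, "data will also be collected from this second admission until 28 days post-study commencement".

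After discharge the protocol provides three things:
- **Telephone call (10.3).** Only for those discharged before day 10. It covers compliance, adverse events, concomitant medication, overall health and the ordinal score.
- **Return visits (9.4, 10.4).** At days 5-10 and 14-28, according to when the patient left hospital, with safety bloods, research samples and an antibody test.
- **Adverse event reporting (12.6).** "The AEs and SAEs reporting period will be from participant consent until 28 days after randomisation". Section 12.2 includes "Any new non-COVID-19 associated conditions detected or diagnosed after the study intervention has been administered to the participant".

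For a patient discharged before day 10, section 7 says that "favipiravir will be supplied and the regimen completed as an outpatient".

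**The concern.** A simple proportion compares the arms fairly only if both are observed for infection over the same period and with similar completeness. Here the stream that would routinely hold a culture result ends when the patient goes home. Discharge is part of the primary endpoint, and shortening the time to it is what favipiravir is hoped to do. If the drug works, its arm spends more of the 28 days outside the stream in which cultures are routinely recorded.

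With no effect on infection, the favipiravir arm could then show a somewhat lower proportion, and a reader might take this as prevention of secondary infection. In the other direction, an excess of infection after discharge would be recorded less completely than one in hospital, including during the days when treatment continues at home.

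**Working it through.** The protocol states no infection rate, length of stay, effect size or power for endpoint 13, so there is no figure to reproduce. The check is first textual, then an illustration on assumed inputs.

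**Step 1: where a culture result would be recorded**

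| Period | Stream | Lists a culture result? |
|---|---|---|
| In hospital | Routine laboratory data (10.2) | Not by name, but covered by laboratory results |
| Readmission to day 28 | Routine data (10.2) | As above |
| Home, discharged before day 10 | Telephone call (10.3) | No |
| Home, discharged before day 14 | Return visits (9.4, 10.4) | No |
| Home, any discharge day, to day 28 | Adverse event record (12.1, 12.2, 12.6) | No; a new condition is reportable if not COVID-19-associated |

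The last row is a real route for post-discharge infection, but a partial one. A secondary pneumonia judged to be COVID-19-associated falls outside the definition. Section 12.1 asks for duration, severity, causality and treatment, not microbiological confirmation. A patient discharged on day 14 or later has neither a scheduled call nor a requested visit, and a visit made early in the day 14-28 window leaves the rest of that window to the adverse event record alone.

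**Step 2: size if nothing after discharge were captured**

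Assumptions, none from the protocol: constant hazard h of a first positive culture, equal in both arms and the same at home as in hospital; exponential stay with mean m; cap at day 28; no deaths; readmission and adverse event capture ignored. The last assumption makes the result an upper bound on the bias for the given stays.

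Proportion observed = h/(h + 1/m) × [1 − exp(−28(h + 1/m))]. With h = 0.008 per day:
- m = 10: 0.0741 × (1 − 0.0486) = 7.0%
- m = 8.5: 0.0637 × (1 − 0.0297) = 6.2%
- m = 8: 0.0602 × (1 − 0.0241) = 5.9%
- m = 7: 0.0530 × (1 − 0.0146) = 5.2%

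| Mean stay, control v favipiravir | Spurious risk ratio | Difference in patients, 250 per arm |
|---|---|---|
| 10 v 8.5 days | 0.88 | 2.2 |
| 10 v 8 days | 0.83 | 2.9 |
| 8 v 7 days | 0.89 | 1.6 |

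With h = 0.004 or 0.012 the first ratio is 0.87 or 0.88, so the ratio hardly depends on the hazard.

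**Step 3: size if part is captured**

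Under the same assumptions the true 28-day risk is 1 − exp(−28 × 0.008) = 20.1% in both arms. If a fraction c of infections after discharge is recorded, the observed proportion is P + c(20.1% − P), where P is the in-hospital figure from step 2. For 10 v 8.5 days:
- c = 0.25: 10.3% v 9.7%, ratio 0.94
- c = 0.50: 13.6% v 13.1%, ratio 0.97
- c = 1: 20.1% in both arms, ratio 1.00

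**Step 4: chance of a false significant result**

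With 250 per arm, no post-discharge capture, true 28-day risk of 5-20% and mean stay of 10 days against 9, 8 or 7, the chance of a nominally significant difference is about 3-13%. The main harm is a shifted estimate.

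**The case against.** The strongest reply is that endpoint 13 is not restricted to hospital. The authors wrote that restriction into endpoint 3 and left it out here; participants are on study for 28 days; and adverse events are reportable to day 28 in both arms. This stands as far as it goes. A reader might infer that endpoint 13 counts only in-hospital infections, or that infections at home would be hidden. The documents support neither: section 10.2 governs one data stream, it resumes on readmission, and a new infection at home that is not COVID-19-associated is a reportable event. What remains is that the endpoint needs culture confirmation, and no contact after discharge is set up to obtain it.

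A reader might also infer from section 9.6, which lists urinary tract infection as a common effect, that infections on home treatment are especially likely to be missed. The protocol's own table does not support that: in Appendix C, urinary tract infection occurred in 1.5% on favipiravir and 1.8% on placebo, and infections overall in 5.0% and 6.6%.

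A further possible inference is that admission cultures taken before randomisation count towards the endpoint. This would rest on silence alone. If they did count, randomisation would balance them on average and they would only dilute a true effect.

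If infections are mainly acquired in hospital, a shorter stay does prevent some, and part of a lower proportion would be a true effect. That is correct, and it reduces the bias computed above.

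Finally, the window could be left to the statistical analysis plan, which is not shown. The definition could be. But an analysis plan cannot recover culture results that no contact was designed to collect.

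**Conclusion.** The point holds in a limited form. Endpoint 13 has no window, follow-up is 28 days, and culture results are captured routinely only in hospital, with adverse event reporting as a partial backstop. Completeness therefore falls after discharge, and the arm discharged sooner can show a lower proportion partly for that reason.

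On the assumed inputs the spurious risk ratio is at most 0.88 for mean stays of 10 v 8.5 days, 0.83 for 10 v 8 and 0.89 for 8 v 7. It moves towards 1 as post-discharge capture improves or if the hazard at home is lower. A larger difference in stay would give a larger bias. In the first scenario it amounts to about two patients per arm of 250.

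This concerns one of 14 secondary endpoints and does not touch the primary analysis. It is worth correcting because it acts in the direction that favours a working drug and is cheap to remove before data are complete.

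**What to change.** Define endpoint 13 as a positive bacterial or fungal culture from a specimen taken after randomisation and up to day 28, regardless of discharge. Add a question on cultures, with a check of the laboratory result, at contacts already planned in both arms: the 10.3 call, the day 5-10 and day 14-28 visits, and the adverse event record to day 28. The last is needed for patients with no later call or visit.

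If post-discharge cultures cannot be obtained, label the endpoint as in-hospital infection and analyse it as cumulative incidence with discharge and death as competing events. That makes its meaning explicit but does not remove its dependence on length of stay, so it should be reported beside length of stay.

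The cost is one sentence in section 6.4 and one eCRF item at existing contacts. The downside is small: some community cultures will rest on patient report and need checking.
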